 - f. For exercise safety purposes, the first exercise session will happen in person, when possible. If not possible, the exercise professional may complete this session virtually by video conferencing. All study supplies (e.g., weights, handouts, exercise logs, protein logs, and protein powder) will be mailed to the participant's home.
2. The exercise and protein log will be used to track the adherence of the patient to the protocol. Patients will be taught to complete the exercise log on the days they perform the exercises at home, along with making any pertinent notes about the exercises and/or how they are feeling. Patients will be taught to complete the protein log daily.
 3. Explain to patients that they should do in-home exercise sessions 2 times weekly until the next Exercise Session with the exercise professional. Patients will complete these exercises alone twice a week. After COVID-19, exercise professionals can offer to work-out virtually with participants once a week.

Table 5. Summary of exercise progression

	Exercise** Session 1	Exercise** Session 2	Exercise** Session 3	Exercise** Session 4	Exercise** Session 5	Exercise** Session 6
SETS	3	3	4	4	5	5
REPS	6	8	8	10	10	10
LOAD*	65%	65%	75%	75%	80%	80%- 85%
REST	30-60 secs	30-60 secs	30-60 secs	30-60 secs	30-60 secs	30-60 secs

*individualized to the patient's strength; **Prior to COVID-19, exercise sessions 1-6 are all in person. After COVID-19, exercise session 1 is in person and sessions 2-6 are virtual.

The exercise professional will meet with the patient for 4-6 Exercise Sessions that will coincide to the degree feasible with their regular infusion sessions. Prior to COVID-19, if scheduling of the Sessions at the clinic is not convenient for the participant, the exercise professional will also be available to conduct these visits at the participant's home. After COVID-19, only Exercise Session 1 is scheduled in person on a day when the participant a clinical appointment, and Sessions 2-6 are conducted virtually via video conferencing. If a participant is not capable of meeting virtually (e.g., lack of technology, internet access or tech skills), the exercise professional will meet the participant in person on the same day as a clinical appointment.

During each follow-up Exercise Session, the exercise professional will:

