1. Collect and review the phone/visit log (these are the same questions asked during the weekly phone call) and exercise log to see what the participant did during the past weeks, discuss barriers, successes, and problem solve if needed. Participants can return logs either in person, over email or by text.
2. Collect and review the protein tracker to ensure that the participant is consuming adequate protein to build lean mass through resistance exercise. Participants can return logs either in person, over email or by text.
3. Visually evaluate the participant's ability to increase weight and adjust the amount of weight appropriately.

In between Exercise Sessions and after the initial 4-6 Sessions, the exercise professional will contact each participant 1 time per week either by phone or video and ask a series of questions

(see Appendix 13.5.5). These calls may be completed through the centralized calling center, by an exercise professional from one of the three study sites. Questions will assess adherence of the patient to the exercise regimen and the pattern of sessions with regard to time between sessions; protein supplement adherence; and any medical complications that prevented exercise sessions from occurring. A contact card will be mailed to participants when they are halfway through the intervention.

Table 6. Intervention Contacts

What	Number of times*	Aim	Time per session
Pre-In Person Training Visit Phone Call	1 time prior to 1 st Exercise Session	Make introductions, orient participant to intervention, obtain health information on participant	20-30 min
Exercise Sessions	4-6 times, every 2-3 weeks during first 3 months of intervention	Learn and progress with exercise protocol	60 min
Home Exercise Sessions	2 times per week	Resistance exercise	45 min
Log Exercise	At-home exercise sessions	Log adherence	5 min
Log Protein Intake	Daily	Log adherence	5 min
Phone or Video Call	Weekly	Track adherence	5 min
Contact Card	1 time	Encourage participation, remind participants to return logs	n/a

*Each cycle is administered every 2-3 weeks

1. The exercise professional will speak with participants to review these exercise and protein logs each week, by phone or video conference, until the intervention is complete at approximately 6 months post initiation (corresponding to completion of adjuvant chemotherapy).

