2. Study staff will then record the adherence of the patients to the exercise regimen and the pattern of sessions with regard to time between sessions, as well as any medical complications that prevent sessions from happening.

Intervention Goals:

Progressively higher weights for resistance training exercises conducted twice weekly throughout intervention) to achieve a 1-kg increase in lean body mass by the end of the intervention.

Intervention Standardization:

All exercise professionals will participate in a multi-day workshop. During this workshop, procedures of the intervention will be explained, and case studies will be presented and practiced. There will be monthly conference calls including all exercise professionals across sites, to monitor and discuss progress, problems and to monitor fidelity of the protocol. Telephone calls to intervention participants to encourage adherence will be scripted.

3.9 Enhanced safety procedures due to COVID-19:

As a result of COVID-19, exercise professionals will adhere to strict safety procedures when meeting with participants for the in person exercise sessions. Enhanced safety procedures include:

- phone screening before visits with COVID-19 script (Appendix 13.2.6),
- temperature checking when entering a clinical facility (KP only),
- both exercise professional and participant wearing face masks,
- frequent hand washing and hand sanitizing,
- maintaining a 6 ft distance when possible,
- frequently wiping down surfaces and equipment with disinfectant wipes, and
- any other appropriate precautions as required by local clinic and hospital procedures.

DFCI exercise professionals will be following DFCI COVID-19 policy for patients and staff while in the building.

3.10 Intervention for the waitlist controls:

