Participants randomized to the usual care (U) group will be instructed to refer to their physician regarding what forms of exercise are safe for them, given their specific medical history. The U group will be told to continue whatever exercise program they have been undertaking up to enrolling in the study, but not to increase exercise or begin weight-lifting over the period of study participation (See Appendix 13.9). Participants will be sent a contact card halfway through the intervention reminding them of the follow-up visit. At the conclusion of participation, they will be offered: Emailed link to WebExercise routine; a set of resistance bands; a 30-minute interview with FORCE exercise professional; and a sample of protein powder.

3.11 Pharmacokinetics study:

Up to 30 individuals, who are scheduled to receive 6 months of 5-FU, leucovorin and oxaliplatin (FOLFOX), will be given the option to participate in pharmacokinetic (PK) testing (see Section 4.14), in addition to the randomized intervention.

3.12 Compensation:

All participants participating at Kaiser Permanente, Penn State and Dana-Farber who are not participating in the PK study will receive a gift card either in person or by USPS as a thank you for completing the baseline visit (\$25) and the follow-up visit (\$25). See Appendix 13.10 for example language to be included in thank card for those gift cards sent by mail. Patients participating in the PK study will receive a total of \$225 in gift cards by study completion- \$100 for each day that PKs are drawn and \$25 for the follow-up visit (total 3 cards). In addition, parking will be validated on the 2 days that PKs are drawn.

3.13 Photographs of study subjects:

Participants will be asked if they would be willing to have their photograph taken. If they are interested, they will be asked to complete the Media Consent form. For those who consent, photographs of study participants will be taken during clinic visits (completing questionnaires, physical assessment testing, talking with study staff), to use in research presentations, for conferences and workshops, where the Investigator(s) present the study. Dana Farber Cancer Institute is excluded from this as they will not ask their participants if they are willing to be photographed.

3.14 Sharing of results with subjects:

All participants will be provided with whole body DXA results, both Baseline and Post-Intervention, after the conclusion of participation (See Appendix 13.8.5).

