7. CRITERIA FOR REMOVAL FROM STUDY

Patients will be removed from study when any of following criteria occur: new invasive cancer diagnosis or recurrence; decision of the participant to stop receiving chemotherapy treatment; request of the patient to withdraw; illness that prevents further administration of the intervention; or study team or treating clinicians deem continued participation not safe for patient. Patients who are removed from study will be asked to complete follow-up assessments if clinically feasible and patients are agreeable. Reason for removal from study will be recorded in patient's study record.

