9.2.1 From Section D. Study overview of the original KPNC application approved 2017

3. How many participants will be enrolled in this study, or how many electronic records or medical records will be used? Provide your best estimate if you are not sure

Number of KPNC participants or records:	Approximately 115 participants to be enrolled
Records used:	Approximately 7500-KPNC records used
Number of non-KPNC participants or records:	Approximately 65 participants enrolled
Total number of participants or records:	Approximately 180* participants enrolled

**Due to the impact of the COVID-19 pandemic on the study, we estimate that the total number of participants will be within the range of 10% above the original total of 180 participants*

9.3 Statistical analysis:

9.3.1 Primary endpoints:

All data analyses will be by intent-to-treat, though in exploratory analyses we will consider compliance to intervention (defined as $\geq 75\%$ of planned sessions) and changes in MM. We will use multiple linear regressions to assess the difference between the intervention and wait-list control groups in mean relative dose intensity (RDI) for each agent and in mean average RDI (ARDI) across all agents. Continuous model covariates will be categorized either as quartiles or into clinically relevant categories (e.g. WHO BMI classification).

Analysis of number of grade 3 and 4 toxicities in relation to randomization arm will utilize Poisson regression given that this outcome can be characterized as a count. These regression models will provide point and interval estimates of adjusted proportional differences in rates of toxicities (expressed as rate ratios) between the control and intervention groups.

9.3.2 Secondary endpoints:

Analyses of inflammatory markers in relation to baseline body composition will utilize multiple linear regression techniques. These analyses of associations at baseline will be conducted in each randomization arm separately, followed by an analysis in the full sample (differences in associations at baseline across arms are not expected).

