### **2.2 Analysis of primary endpoints**

## Statistical Analysis Plan

FORCE: Focus on Reducing Dose-Limiting Toxicities in Colon Cancer with Resistance Exercise

All data analyses will be by intent-to-treat. Multiple linear regression will be used to assess the difference between the RT and UC groups in RDI. We will analyze RDI individually for each drug and then across all chemotherapy regimens combined. We will use logistic regression to examine the commonly used cut points < 85% and <70% RDI as outcomes.

We will assess the difference between RT and UC groups in self-reported treatment toxicities in three ways:

- A. as a binary variable with yes as the occurrence of any of one of 8 symptoms that are reported as moderate or severe over the course of chemotherapy in RT vs. UC. We will exclude the PRO-CTCAE muscle ache item from the composite score (will be reported separately), since that is believed to be related to the performance of the resistance training intervention. We'll utilize logistic regression for point and interval estimation of odds ratios, RT vs. UC, for any (i.e., one or more) of 8 symptoms reported as moderate severe, for each symptom individually, and finally in groups of similar symptoms, such as gastrointestinal issues;
- B. as the number of the 8 symptoms reported as moderate or severe at least once over the course of chemotherapy in RT v. UC (a count ranging from 0-8). We will use Poisson regression with allowance for overdispersion for point and interval estimation of relative differences (rate ratio) in the mean total number of moderate or severe toxicities reported at least once over the course of chemotherapy; and
- C. as longitudinal analyses of number of moderate or severe toxicities reported per cycle in relation to randomization arm (RT vs. UC) and time since randomization using Poisson regression with allowance for overdispersion. Generalized estimation equations (GEE) will be used for model parameter estimation to account for within person correlation in repeated measures. The main effect for randomization arm is interpreted as the average treatment effect over the time. Heterogeneity in effect over time will be assessed by inclusion of randomization arm by time-interaction terms.

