In addition to treatment arm, each model will include covariates used in the randomization procedure (study site, treatment duration, treatment regimen, gender, stage). Exploratory analyses will examine the impact of including additional (not pre-specified) covariates in estimation of treatment effect, with a focus on variables with chance imbalance in distributions by treatment group. Analyses resulting in an appreciable change in the estimate of between-group differences or increase in precision of the treatment effect will be noted.

We will also conduct analyses stratified by sex, frailty status and duration of the intervention, excluding the strata-variable from the covariate list (i.e., exclude gender in analysis by men and women) by inclusion of appropriate cross product terms in regression models. Exploratory analyses will additionally assess heterogeneity in treatment effect on study outcomes by exercise adherence.

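### Exploratory heterogeneity of treatment effect by exercise adherence conditions on a post-randomization variable that exists only in the exercise arm, so it can show an apparent benefit in adherers even if exercise has no effect

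*SAP*

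**What the plan says.** The SAP, section 2.2, sets the primary frame as "All data analyses will be by intent-to-treat". It then plans analyses by sex, frailty status and intervention duration using cross-product terms, and adds: "Exploratory analyses will additionally assess heterogeneity in treatment effect on study outcomes by exercise adherence". The available SAP text does not define adherence, name a comparator, give a model or caution on interpretation.

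Protocol 9.3.1 likewise qualifies intent-to-treat: "in exploratory analyses we will consider compliance to intervention", with compliance set at 75% or more of planned sessions. It does not say whether the number of planned sessions is fixed at the start or shrinks when chemotherapy is shortened.

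Other parts of the documents bear on this:

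- Protocol 3.8, data source: "The exercise and protein log will be used to track the adherence of the patient to the protocol". The log is issued to RT participants at Exercise Session 1.
- Protocol 3.8, weekly calls: these ask about adherence and about "any medical complications that prevented exercise sessions from occurring". Staff then record adherence together with "any medical complications that prevent sessions from happening".
- Protocol 3.10, controls: they may continue their existing exercise, "but not to increase exercise or begin weight-lifting over the period of study participation". They have no planned sessions.
- Protocol 7: removal criteria include "decision of the participant to stop receiving chemotherapy treatment" and illness that prevents the intervention from continuing.
- SAP introduction and 1.1: the intervention runs until two weeks after the last chemotherapy cycle, and RDI counts reductions, delays and early stopping.

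**The concern.** Sex and planned duration exist in both arms and are fixed before randomization, so the treatment effect can be compared across their levels. Adherence has neither property. There is no adherent control group, and those who would have adhered if assigned to RT cannot be identified among the controls.

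The documents also describe a route by which the outcome and adherence can share a cause. Illness during chemotherapy can prevent sessions, and the same illness can lead to dose reduction, delay or stopping, which lowers RDI. If the session denominator is fixed, early stopping also lowers measured adherence directly; if it shrinks with treatment, it does so less. Either way, RT patients who complete their sessions may be those who were going to tolerate chemotherapy better.

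At stake is the interpretation of a null or weak intent-to-treat result. A split by adherence could then be read as showing that exercise works when it is done, when the pattern reflects who was able to exercise. Calling the analysis exploratory lowers its standing but does not reduce this bias.

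**Working it through.** **Inputs from the documents.** 92 RT and 91 UC (SAP 2.1); RDI SD 17.3, two-sided alpha 0.05, power 0.80, 90 planned per arm, detectable difference 0.42 SD or 7.3 points (Protocol 9.3.4 and SAP 2.1).

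**Inputs assumed.** Share of RT patients who are adherent, p (0.65 in the main case, 0.5 to 0.8 as range). Correlation between latent adherence and the patient's own RDI, rho (0.1 to 0.5). The documents give neither.

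**Step 1: the plan's yardstick reproduces.** n per arm = 2 × (1.960 + 0.842)² / 0.42² = 89, against 90 planned. 0.42 × 17.3 = 7.27, stated as 7.3.

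**Step 2: identification.** Write RDI = a + b1·R + b2·A + b3·R·A, with R = 1 for RT and A for adherence. UC has no value of A. If A is set to 0 in UC, then R·A = A for every patient, and b2 and b3 cannot be separated. What remains is a comparison of self-selected RT patients with all of UC.

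**Step 3: bias when exercise does nothing.** Take latent adherence as normal, and call the top share p of RT the adherers. Then, relative to UC:

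- adherers: +rho × SD × φ(z_p) / p
- non-adherers: −rho × SD × φ(z_p) / (1 − p)

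For p = 0.65, z_p = 0.385 and φ(z_p) = 0.370. With rho = 0.3:

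- adherers: 0.3 × 17.3 × 0.370 / 0.65 = +3.0
- non-adherers: −0.3 × 17.3 × 0.370 / 0.35 = −5.5

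**Step 4: how often it would be significant.** Simulated null trials (20,000 per row, 92/91, p = 0.65, two-sided 5% tests; false benefit counts only significant results favouring adherers):

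| rho | Adherers v UC | Non-adherers v UC | Significant false benefit, adherers v UC | Significant difference, adherers v non-adherers |
|---|---|---|---|---|
| 0 | 0 | 0 | 2.5% | 5% |
| 0.1 | +1.0 | −1.8 | 5% | 11% |
| 0.2 | +2.0 | −3.7 | 10% | 31% |
| 0.3 | +3.0 | −5.5 | 17–18% | 61% |
| 0.5 | +4.9 | −9.2 | 41–42% | 97% |

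Over p from 0.5 to 0.8 at rho = 0.3, the bias in adherers is +4.1 to +1.8 points, the false-benefit rate 27% to 10%, and the rate for adherers versus non-adherers 64% to 52%. At rho = −0.2 the sign reverses and adherers look 2.8 to 1.2 points worse. The intent-to-treat test stays near 5% throughout.

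**Step 5: a randomization-based alternative.** With controls at zero sessions, the instrumental-variable estimate is the intent-to-treat difference divided by mean adherence. It is zero when the intent-to-treat effect is zero. Its detectable difference is about 7.3 / mean adherence: 14.6 at 0.5, 11.2 at 0.65, 10.4 at 0.7, 9.1 at 0.8.

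**Step 6: why not instrument the 75% cut.** Patients below the cut still exercise. As an illustration (assumed): a full-dose effect of 5 points, mean dose 0.9 in adherers and 0.4 in non-adherers, 65% adherent. The intent-to-treat effect is 5 × (0.65 × 0.9 + 0.35 × 0.4) = 3.6. Divided by 0.65 it gives 5.6, whereas the effect in adherers is 5 × 0.9 = 4.5.

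**The case against.** The strongest reply is that the sentence is exploratory, primary inference is intent-to-treat, and no method is stated. The cross-product wording belongs to the sentence on sex, frailty and duration, so a valid approach such as a complier-average or principal-stratum analysis is not excluded. That stands: the primary result and its error rate are untouched, and part of the defect is under-specification. It does not rescue the planned quantity, because heterogeneity of treatment effect by adherence is not identified by the randomization under any coding of the controls.

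A reader might infer that the analysis is bound to show a benefit in adherers. The documents do not support that. Size and sign depend on a correlation and an adherent share that they do not report, and at rho = 0.3 with 65% adherent the large majority of null trials show no significant benefit versus control. The 61% figure is the contrast within RT and should not be read as the rate of false benefit against control.

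A reader might also infer that toxicity determines adherence. The protocol says only that complications preventing sessions are recorded. A link is a reasonable inference, but its strength is unknown, and the recorded reasons could help separate medically missed sessions from others.

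A last objection is to the instrumental-variable remedy. RT also includes protein powder and weekly contact, which may act regardless of sessions done, and controls may continue existing exercise. These are real threats to its assumptions, so it should be optional.

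**Conclusion.** The concern holds as a defect in a secondary, exploratory analysis. The planned contrast conditions on a variable that arises after randomization, exists in one arm only and is likely related to chemotherapy tolerance. It can produce an apparent benefit in adherers, and apparent heterogeneity, with no exercise effect. The main-case bias of +3.0 points in adherers is about 40% of the trial's own detectable difference (3.0 / 7.3 = 0.41). Apparent heterogeneity within RT is the more inflated of the two signals.

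The sizes rest on an SD of 17.3 for RDI, normal latent adherence, and assumed rho and p. The lack of identification rests on none of these. It follows from the design.

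**What to change.** 1. Remove exercise adherence from the treatment-effect heterogeneity analyses in SAP 2.2, and align Protocol 9.3.1.
2. Define adherence as the fraction of planned sessions completed, with the denominator fixed at randomization.
3. Report adherence, the recorded reasons for missed sessions, and the association of adherence with RDI and toxicity outcomes within RT only, labelled descriptive and non-causal.
4. Optional: if an effect-of-adherence estimate is wanted for RDI or ARDI, use two-stage least squares with randomized arm as instrument for the continuous session fraction, adjusted for the randomization factors. State that protein supplementation, weekly contact and control-arm exercise may violate its assumptions. Do not use the 75% cut as the instrumented exposure.

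The cost is a short SAP edit and a few lines of code on data already collected. The trial gives up a subgroup-style adherence result, and the optional estimate has wider intervals than a simple split. Because that estimate tests essentially the same null as intent-to-treat, it adds scale and not power.
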